9.4.16 Data Recording

The prover will be expected to make a daily record of the date and time of intake of study medication in the prescribed proforma. During the 3 day study medication intake period, the prover will report to the investigator daily. The investigator will interrogate the prover about the change in health status/sign and symptoms if any during this period and will record his/her observations in the symptom elaboration proforma (**Form F & G**).

Each symptom must be completed with respect to order of appearance, time of appearance & disappearance, location, sensation/character, modalities, concomitants, direction/extension of symptoms, etc. Clinical examination findings will also be recorded. Appropriate pathological investigations if required would also be advised and the report will be added. For each symptom, the investigator on detailed interrogation with the prover, will classify and mention their symptoms as follows^[9]:

- **NS** - New symptoms, not previously experienced.
- **C-** - Unexpected change representing worsening or aggravation of ongoing or recurring symptoms.
- **C+** - Unexpected change representing an improvement of ongoing or recurring symptoms.
- **RS** - Unexpected recurrence of past symptoms.

The investigator will also record his/her observation about the possible causality of symptoms with the drug intake.

9.4.17 Follow up:

A. If sign(s)/symptoms(s) appear:

- The prover must stop taking the further dose of study medication as soon as he/she feels any change in health status or any sign(s) &/or symptoms(s) develop in accordance with the qualifiers of proving symptoms as described in section 13.2. The investigator will ascertain the qualifiers of the symptom and will advise the prover to stop intake of further doses, once proving symptoms develop.
- The prover notes down the sequence of the appearance of new sign(s) &/or symptoms(s), their progress and the number of doses after which each sign &/or symptom appears with date, time of onset and duration for which it persists. No further dose of the same batch is to be consumed by the prover.
- The prover is expected to report (preferably on a personal visit or telephonically) to the investigator daily (or more frequently) for as long as the symptoms persist.

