13.4 Compilation of Proving symptoms

The sign(s) &/or symptom(s) generated in each prover after the end of each drug batch will be noted along with their prover code, name of the proving center, number of doses after which each of the signs or symptoms appeared and the duration for which they persisted. The sign(s) &/or symptom(s) generated in the drug group will be segregated from those of the control group. In the intervention group sign(s) &/or symptom(s) generated during intake of placebo batch will be segregated from those appearing during IP intake. The sign(s) &/or symptom(s) which are identical (exactly the same in terms of location, sensation, modalities, concomitants) in both drug and placebo will not be included as proving symptoms.

These proving symptoms will be identified. These proving symptoms will be compiled and arranged as per the schema of the Kent's Repertory i.e. Mind, Vertigo, Head, Eye, Ear,etc.

To each sign and symptom generated, the following information will be linked:

- Prover code: Number
- Prover gender: M/F
- Proving Center: XX
- Day of symptom appearance (Day 1 being the day of administration of the study medication batch)
- Time of day of symptom occurrence (HH:MM) *(if information available)*
- Characterizing feature(s)
- Duration for which the symptom persisted in terms of hours/days
- Potency of the IPS in the study medication batch

This information would then be the basis where the following types of symptoms are distinguished:

- Characteristic symptoms (if reported)
- Ongoing symptoms that have unexpectedly and markedly improved
- Proving symptoms with one or more characterizing features

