14. DATA ANALYSIS

14.1 Qualitative analysis:

14.1.1 Symptom selection criteria:

Drug proving data is in the form of symptoms, where there is no measure of efficacy, but description of individual proving symptoms where qualitative research evaluation will be applied. The evaluation will be done by compilation of the proving symptoms in different categories, representing a certain probability to be associated with the remedy and therefore are the most important ones for further clinical verification.

Example: a symptom will belong to the remedy with great probability if at least one of the following criteria is met^[5].

- Occurrence of the symptom in two or more volunteers
- Objective, measurable signs corroborating with the symptoms
- Distinct intensity of the symptom
- Occurrence of the symptom several times shortly after administration of the drug
- Recurrence of the symptom several times over the course of a number of days
- Recurrence of the symptom using different potencies
- Striking, singular, uncommon symptoms
- Striking, seldom or paradox modalities and/or concomitants of the symptom

However, all symptoms including those appearing in lesser number of provers, less distinct or common symptoms will all be included in the proving data. Symptoms, which are not thought to belong to the drug picture, would also be stated, but under separate headings, marked in a specific manner so they are not lost for clinical verification. Such symptoms may be compared with the clinical verification symptoms at a later stage if required.

14.1.2 Characterizing features of proving symptoms:

All provers are to be included in the analyses. The symptoms obtained under verum or placebo must be listed separately. The proving symptoms are identified and their characterizing feature^[9] will be detailed:

- A.** New symptoms with marked severity, duration or frequency
- B.** Ongoing or recurring symptoms present during the proving that have been unexpectedly and markedly improved
- C.** Ongoing or recurring symptoms that have been unexpectedly and markedly worsened
- D.** Symptoms that recur from the past but have not occurred in the 12 months preceding the proving
- E.** Symptoms that display alteration with another symptom in a single volunteer in such a way that the alteration is strongly individualizing
- F.** Symptoms associated with modalities or concomitant symptoms occurring in other parts of the same prover

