	2							
	3							
	4							
Day 2	1							
	2							
	3							
	4							
Day 3	1							
	2							
	3							
	4							

PROVER'S SIGNATURE

* Prover must write in own language. Avoid all medical terms. Elaborate the symptom as vividly as possible
 ° Intensity of the symptom: Mark your symptom on a scale of 1 to 10, where 1 is very low/slight and 10 is extremely bothersome

Form F

SYMPTOM ELABORATION PROFORMA

(to be filled by SITE INVESTIGATOR)

INSTITUTE/ UNIT

CENTRAL COUNCIL FOR RESEARCH IN HOMOEOPATHY, NEW DELHI

General instructions:

- Write legibly.
- Do not use any abbreviations.
- Write complete sentences.
- Record verbatim conversation with the prover.
- In table – 1 record the detailed conversation held with the prover “verbatim”. From the symptoms detailed in table – 1 and further clarifications made with the prover, complete each individual symptom in table 2
- Query for all details related to circumstances, environmental factors, climatic conditions.
- Attempt to complete the symptoms in all possible aspects
- Avoid all medical and technical terms. Explain each term used as vividly as possible.
- Identify intensity of symptoms on a VAS scale on a scale of 0-100mm. Attach sheets with VAS scale separately
- Under the heading of classification of symptoms (\$): Classify the symptoms as follows after complete questioning with the prover & taking into consideration the previous recordings made with the prover during the PME & run-in phase:
 - New symptoms, not previously experienced (NS)
 - Unexpected change representing worsening or aggravation of ongoing or recurring symptoms (C-)
 - Unexpected change representing an improvement of ongoing or recurring symptoms (C+)
 - Unexpected recurrence of past symptoms (RS)

Name of the Prover.....Proving Code No. CCRH/.....Batch No.....

Face to face reporting by the prover:

Date	Time	Date	Time	Date	Time

Telephonic reporting by the prover

Date	Time	Date	Time	Date	Time

Table - 1

Date	Time of administration of the drug	Verbatim record of symptoms(s)/ any change in bodily functions/change in mental state experienced by the prover in order of their appearance as detailed by the prover

Symptom segregation, completion & development of chronology of complaints

Table - 2

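### Symptom intensity is collected on two unreconciled scales and neither score reaches the compiled record, while the *distinct* and *marked* calls that rest partly on it are tied to no score and come after de-coding

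*Protocol*

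**What the plan says.** Intensity is recorded in two places. In Form E Part 2, the diary for the drug intake period, the prover is told: "Mark your symptom on a scale of 1 to 10, where 1 is very low/slight and 10 is extremely bothersome". In Form F, headed "to be filled by SITE INVESTIGATOR", the general instructions say: "Identify intensity of symptoms on a VAS scale on a scale of 0-100mm. Attach sheets with VAS scale separately". Table 2 of Form F, where each symptom is completed, has no intensity column.

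Section 13.4 lists what is linked to each symptom when the data are compiled: prover code, sex, centre, day of onset, clock time, characterizing features, duration and potency. Duration is specified as "Duration for which the symptom persisted in terms of hours/days". No intensity score is listed.

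Section 14.1.1 gives, as an example, eight criteria, any one of which makes it highly probable that a symptom belongs to the remedy. The third is "Distinct intensity of the symptom". Section 14.1.2 lists nine characterizing features, A to I. Feature A covers new symptoms of marked severity, duration or frequency. Feature B is "Ongoing or recurring symptoms present during the proving that have been unexpectedly and markedly improved", and C is its counterpart for worsening.

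Section 13.3 orders compilation in four phases: (1) the medical examinations, (2) entry of symptoms by prover and batch, (3) de-coding and separation of verum from placebo symptoms, (4) analysis, matching and compilation of the pathogenesis.

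**The concern.** The analysis is mainly qualitative, so the decision that a symptom is *distinct* or *marked* is part of the result: it helps settle what enters the drug picture. The blinding is useful only if such decisions are made, or can be checked, without knowledge of allocation. Here a measurement that could anchor them is taken twice, on scales with different ranges, and is then not among the fields that accompany each symptom into the analysis. The rules that would use it do not mention it.

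Two things are at stake. The first is bias: once the codes are open, a verum symptom can more readily be judged distinct than a similar placebo one. The second is reproducibility: a second analyst holding only the compiled data could not repeat the call. Going back to the forms would yield two scores and no statement of which one counts.

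**Working it through.** The protocol gives no figure on this point to reproduce. The check sets its parts side by side, with one small illustration.

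**1. The two scales**

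| | Form E Part 2 | Form F |
|---|---|---|
| Range | 1 to 10 | 0 to 100 mm |
| Lowest point | 1, slight | 0, no anchor given |
| Rater | prover | not stated; the form is completed by the site investigator |
| Where it sits | diary column | separate sheets, no column in Table 2 |
| Rule linking it to the other | none | none |

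**2. How far the scales can diverge on conversion alone**

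The protocol gives no conversion, so two linear ones are assumed for illustration. For a prover score *s*:

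- Conversion 1: 10 × *s* mm
- Conversion 2: 100 × (*s* − 1)/9 mm

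Results:

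- *s* = 1: 10 mm against 0 mm, difference 10 mm
- *s* = 5: 50 mm against 44.4 mm, difference 5.6 mm
- *s* = 10: 100 mm against 100 mm, difference 0 mm

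The same prover score moves by 0 to 10 mm with the conversion chosen, most at the low end. Any disagreement between raters would add to this, and the protocol gives no basis for sizing it.

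**3. What is carried forward**

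Of the eight linked fields in 13.4, none is an intensity score (0 of 8). The nearest is the characterizing-features field, which can hold the conclusion that a symptom was marked but not the measurement behind it.

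**4. What depends on intensity**

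- 14.1.1: one of eight example criteria, sufficient on its own.
- 14.1.2 A: in part. It is also met by marked duration or frequency, and duration is a compiled field.
- 14.1.2 B and C: in part. Improvement or worsening may be in severity, but section 13.2 also names duration and frequency.
- None of these rules cites either scale.

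**5. Order of events**

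De-coding is phase 3 and analysis is phase 4. Section 13.4 likewise describes the separation of drug from placebo symptoms before it lists the fields to be linked. The protocol does not say that the intensity calls are made earlier, or by someone kept blind.

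**6. Telephone contacts**

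Under 9.4.17, while symptoms persist, "The prover is expected to report (preferably on a personal visit or telephonically) to the investigator daily". Form F has its own log of telephone reports. No instruction says how the visual analogue rating is obtained at such a contact.

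**The case against.** The strongest reply is that intensity is well documented. It is recorded twice, and under 13.3 the original Forms E and F go to the coordinators at headquarters. The site investigator, who is blind, classifies each symptom as new, worsened, improved or recurrent under 9.4.16, using earlier records from the pre-trial examination and run-in. The characterizing features, including marked change, are themselves a compiled field. A self-rating beside a second scale on the investigator's form is not a contradiction, and numeric cut-offs may sit in an analysis plan that is not shown. The 14.1.1 list is only an example, the same section keeps less distinct symptoms in the proving data, and neither the grading in 14.1.3 nor the incidence measures in 14.2 call for an intensity score.

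Most of this stands, and it rules out several stronger readings:

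- A reader might infer that intensity cannot be measured. It is measured, on both forms.
- A reader might infer from the missing zero that full resolution cannot be recorded. The scale rates a symptom that is present. Absence is entered in words (9.4.15), and both forms time disappearance.
- A reader might infer that the visual analogue scale cannot be used by telephone. No text says who marks it or bars it; there is simply no procedure.
- A reader might count A, B and C as three intensity rules out of nine. Each can be met on other grounds.
- A reader might infer that ongoing complaints have no pre-dose score. Only Part 2 of Form E is shown, so this cannot be judged.

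The reply does not supply a governing scale, put a score in the compiled record, or place the *distinct* and *marked* calls before the codes are opened. The blinded site classification gives the direction of change, not whether it was marked. Even if cut-offs are set elsewhere, the forms, the 13.4 list and the phase order are fixed in this protocol.

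**Conclusion.** The point holds in limited form. Two intensity scores are collected without a statement of which governs, and neither is among the 13.4 fields. One of eight example criteria, and features A to C in part, are tied to neither score and are applied after de-coding. Those calls can be made with allocation known and cannot be reproduced from the compiled data alone.

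The size is modest: only symptoms admitted on distinct intensity, or on the severity element of A to C, are affected. Their number cannot be estimated from the protocol. The conclusion rests on reading the phase numbers in 13.3 as the order of work. The sentence there on un-blinding is loosely worded about where phases 1 and 2 fall, but on either reading phase 4 comes after the codes are broken. Nothing here shows that the calls will in fact be biased; the plan leaves them open to it when a cheap safeguard is available. This is a worthwhile low-cost improvement, not a defect that invalidates the analysis.

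**What to change.** 1. Name one of the two existing scales as governing. State who rates it and how it is taken at a telephone contact. The other may stay as supporting information; the visual analogue scale need not be withdrawn.
2. Add the governing score to Form F Table 2 and to the linked fields in 13.4: the score at onset, the worst score and, for ongoing complaints, the pre-dose score where one is recorded.
3. State a rule, chosen and justified by the sponsor, by which that score gives the *distinct* call and the severity part of *marked*. No particular cut-off is proposed here.
4. Make these calls in phase 2 of 13.3, before the codes are broken, and word the un-blinding sentence so that this order is plain.

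The cost is one more item to compile (up to three values per symptom), edits to a form instruction, one table and one list, and a reordered compilation step. Both scales are already in use, so no new instrument is needed.
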